## 2.2. Effect of Antenatal Corticosteroids on Neonatal Morbidity

In 2016 an important step toward reducing respiratory morbidity in neonates born in the late preterm period occurred. A study of 2827 late preterm pregnancies showed a significant reduction in respiratory complications among neonates exposed to BMZ in utero compared to placebo (11.6 v 14.4%,  $p=0.02$ ), however, neonatal hypoglycemia was more common in the BMZ compared to placebo group (24% vs 15%,  $p<0.001$ ). There was no significant reduction in NICU admission (41.8 v 44.9%,  $p=0.09$ ), suggesting that there is potential for additional improvement in late preterm neonatal outcomes. Other studies have also demonstrated an increase in neonatal hypoglycemia after exposure to BMZ, although the mechanism has not yet been studied.

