### 4.4. Patient Management and Follow-up

Other than the timing and frequency of maternal glucose screening and recommended thresholds for treatment of hyperglycemia detailed in the study protocol, women will receive standard care as defined by their clinical provider. Women randomized to the intervention arm will undergo screening for and treatment of maternal hyperglycemia until delivery or hospital discharge for a maximum of 5 days following BMZ.

All study neonates will have CBG testing within 2 hours of life. This is standard of care for neonates born at less than 37 weeks. As part of the study protocol, CBG will be measured within 2 hours of life on those neonates who are delivered at or after 37 weeks and 0 days. The remainder of neonatal care will be according to the clinical provider. Umbilical cord blood and placental samples will be collected after delivery to evaluate fetal metabolic status in utero as well as other genetic changes. All study specimens will be labeled with a unique study ID code. Personnel responsible for lab assays will receive the specimens in a coded fashion without any documentation of PHI or study arm.

- Placental biopsies:
  - 15 punch biopsies will be obtained from each placenta using a standard 3mm punch biopsy tool. Biopsies should be obtained 2 cm from the cord insertion site.
  - Three punch biopsy samples will be placed into 5 separate aliquot tubes.
  - 0.5mL AllProtect solution will be placed in 3 of the 5 aliquot tubes
  - The other 2 aliquot tubes will be empty
- Placental portions:
  - 2 placental portions should be removed using sharp dissection (scalpel or scissors). Each portion should measure approximately 0.5 by 0.5 inches and should traverse the complete depth of the placenta.
  - Each placental portion should be placed into a 15mL falcon tube
  - The distance from the cord insertion should be recorded. One portion should be removed 2 cm from the cord insertion. The other should be removed 2 cm from the periphery.

While maternal CBG will only be performed for maximum of 5 days following BMZ, maternal postpartum data will be collected through hospital discharge. Neonatal data will be collected through hospital discharge or until 28 days of life.

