#### 4.6. Study Outcome Measures and Ascertainment

##### 4.6.1. Primary Outcome

**Fetal C-peptide levels (in mg/dL), measured in umbilical venous blood**

##### 4.6.2. Neonatal Secondary Outcomes

1. Fetal cortisol, insulin-like growth factor, leptin, and other hormonal and metabolic markers
2. NICU admission and length of stay
3. Neonatal hypoglycemia, defined as CBG < 40mg/dL within the first 48 hours of life
4. Neonatal blood glucose nadir (in mg/dL)
5. Timing of neonatal blood glucose nadir (in minutes of life)
6. Severe neonatal hypoglycemia, defined as composite of:
  - a. CBG < 25mg/dL at 0-4 hours of life
  - b. CBG < 35mg/dL at 4-24 hours of life
7. Symptomatic hypoglycemia, defined as CBG < 40 and one of the following: poor feeding, irritability, tremors, jitteriness, exaggerated Moro reflex, lethargy, seizure, poor tone, persistent hypothermia
8. Neonatal hypoglycemia treatment (i.e. measurable feeding, glucose gel, glucose-containing IVF)
9. First repeat neonatal blood glucose after treatment
10. Seizures or encephalopathy due to hypoglycemia
11. Neonatal mortality

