**Analysis Plan for Aim 2 (BMZ-exposed subjects in usual care group vs intervention group):**

Cord blood C-peptide levels will be compared between randomized arms (usual care vs. screening/treatment after BMZ) using a linear model, controlling for gestational age at randomization. We will estimate the mean difference between groups along with a 95% confidence interval. Similar models will be used to compare 2° metabolic measurements such as cord blood cortisol, insulin-like growth factor, and leptin levels between BMZ-exposed usual care vs. BMZ-exposed intervention group. Metabolic and hormonal analytes will be correlated with our exploratory outcomes: neonatal hypoglycemia (defined as neonatal glucose < 40mg/dL within 48 hours of birth), NICU admission, and NICU stay  $\geq$  72 hours.

If the 2 groups show a difference in the 1° outcome, interactions will be evaluated using linear regression models and subgroup analyses conducted to determine whether the effect differs across particular subgroups of patients. In particular we will assess subgroups defined by gestational age (dichotomized at 36 wks), interval from BMZ exposure to delivery (dichotomized at 3 days), maternal obesity (defined as BMI  $\geq$  30 kg/m^2 at time of delivery), race/ethnicity, and expected indication for late preterm delivery at trial entry (preterm premature rupture of membranes vs. preterm labor vs. obstetrical/medical indication). We will conduct 2° analyses to examine neonatal sex (male vs. female) on the 1° outcome.

We will use linear regression models to assess the association between randomization arm, time since first dose of BMZ until delivery, doses of BMZ received, and the interactions of the latter two with each of the study arm approaches (usual care vs. screening/treatment). We will estimate the association between time interval to delivery and number of BMZ doses separately in each study arm and compare the associations between arms.

Loss to follow-up will be defined as the inability to ascertain whether the neonate was born alive and if born alive umbilical cord blood not collected. Those defined as lost to follow-up will not be included in the primary analysis. It is expected that the loss to follow-up rate will be very low, less than 10 percent. However, a sensitivity analysis will be performed including patients lost to follow-up with “worst case” assumptions regarding their outcome to determine whether the results are robust.

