## 2. Data Collection

### 2.1. Data Collection Forms

Data will be collected on standardized forms on which nearly all responses have been pre-coded. Each form is briefly described below:

- Randomization and Baseline Characteristics Log - completed for all randomized patients and records project gestational age, assigned study number, and information on the management arm.
- Maternal Demographics - includes detailed maternal demographics, social data, and history.
- OB History – includes detailed obstetric history
- Maternal Glucose Log - documents maternal blood glucose measurements and any insulin administered prior to delivery.
- Labor and Delivery Summary - documents specific pregnancy complications since randomization, labor, delivery and postpartum information.
- Neonatal Baseline Form - records date and time of birth, delivery data and status at delivery, for each neonate.
- Neonatal Glucose Log - records neonatal blood glucose measurements and any treatments required for hypoglycemia
- Patient Status Form - documents loss to follow-up/withdrawal status, last date of contact for lost to follow-up patients, and side effects since the last dose of steroids.
- Adverse Event Form - records adverse events.

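### Aim 2 relates cord analytes to infant glucose only through a yes/no cut at 40 mg/dL; adding the logged glucose values would cheaply strengthen this exploratory analysis

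*Combined protocol and SAP*

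**What the plan says.** The Analysis Plan for Aim 2 (under section 5.3 in the contents list, printed as 1.1) states that "Metabolic and hormonal analytes will be correlated with our exploratory outcomes: neonatal hypoglycemia (defined as neonatal glucose < 40mg/dL within 48 hours of birth"). The sentence goes on to "NICU admission, and NICU stay" of at least 72 hours. All three outcomes are yes/no. The text calls them exploratory and gives no test, expected correlation or power for them.

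Other sections describe the same infant measures on a fuller scale:

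- Section 4.6.2, item 4, lists "Neonatal blood glucose nadir (in mg/dL") as a secondary outcome. Item 2 lists "NICU admission and length of stay".
- The Data Collection Forms section (6.1 in the contents list, printed as 2.1) describes a Neonatal Glucose Log that "records neonatal blood glucose measurements and any treatments required for hypoglycemia".
- Section 4.4 fixes one reading for everyone: "All study neonates will have CBG testing within 2 hours of life". Other neonatal care is left to the provider.

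No section relates the analytes to the nadir or to the 2-hour value.

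**The concern.** The primary outcome, cord C-peptide, is a surrogate. Section 2.3 argues that fetal hyperinsulinemia leads to low glucose at birth, and section 2.4 presents the trial as groundwork for a larger one. The analyte correlations are the only planned analysis of that last step, from cord blood to infant. Section 3.2 also asks about the degree of hypoglycemia, which a single cut discards.

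A cut at 40 mg/dL treats readings of 41 and 80 alike, and likewise 39 and 20. If C-peptide does track neonatal glucose, the yes/no version is more likely to miss it. The plan reports non-significant tests as inconclusive, so the study could finish without an answer that its own glucose log might have given.

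**Working it through.** **Inputs.** Evaluable infants: 130, and 100 for delivery within 3 days (section 5.1, Table 4). Alpha: 0.05 (Table 4), taken as two-sided because sidedness is not stated. Hypoglycemia: 24% with betamethasone and 15% with placebo in the earlier trial (section 2.2). Correlation r between analyte and glucose: not in the documents, so a range is shown. Both arms are assumed pooled.

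**The plan's own figure.** No power is stated for the correlations. The nearest figure is the bold row of Table 4 (difference 1, SD 1.5). Power is Φ(d/(s√(2/n)) − 1.96) with n per group:

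- n = 65: 1/(1.5 × 0.1754) = 3.80, and Φ(1.84) = 96.7% (stated 95%).
- n = 50: 1/(1.5 × 0.20) = 3.33, and Φ(1.37) = 91.5% (stated 90%).

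Both agree within 2 points, so two-sided 0.05 with these sample sizes is a fair basis.

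**Step 1: what the cut keeps.** Cutting a normal variable so that a share p falls below the cut multiplies the correlation by φ(z_p)/√(p(1−p)). For p = 0.24, z = −0.706 and φ = 0.311, so 0.311/√(0.24 × 0.76) = 0.311/0.427 = 0.728. Squared, that is 0.53, as if about 0.53 × 130 = 69 infants had been used.

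**Step 2: power.** Power = Φ(atanh(r)·√(n−3) − 1.96), with r replaced by 0.728r for the cut. At n = 130 and r = 0.20:

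- Nadir: 0.2027 × 11.27 − 1.96 = 0.325, giving 62.7%.
- Cut: r becomes 0.146, and 0.1466 × 11.27 − 1.96 = −0.307, giving 37.9%.

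Results at a 24% rate and n = 130 (losses from unrounded values):

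| True r | Nadir (mg/dL) | Glucose < 40 | Loss (points) |
|---|---|---|---|
| 0.10 | 20.3% | 12.8% | 7.6 |
| 0.15 | 39.9% | 23.4% | 16.4 |
| 0.20 | 62.7% | 37.9% | 24.8 |
| 0.25 | 82.1% | 54.5% | 27.5 |
| 0.30 | 93.7% | 70.6% | 23.1 |
| 0.35 | 98.5% | 83.5% | 14.9 |
| 0.40 | 99.8% | 92.2% | 7.6 |
| 0.50 | 100.0% | 99.0% | 1.0 |

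**Step 3: checks.**

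- Simulation (2,000 runs per cell, r = 0.20 to 0.30) gives a loss of 24 to 26 points by Pearson, and 21 to 22 if the nadir is analysed by Spearman.
- At n = 100 and 24%, the loss for r = 0.20 to 0.30 is 21 to 27 points.
- If the intervention removed the whole betamethasone excess, the pooled rate would be (24 + 15)/2 = 19.5%. At 20% and n = 130 the loss is 27 to 31 points.

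**Step 4: NICU outcomes.** Simulating stay as zero for infants not admitted (42% admitted, in line with the 41.8% in section 2.2) and testing by ranks, length of stay gains about 1 to 6 points over NICU admission. Over the 72-hour cut it gains about 6 to 18 points for r = 0.20 to 0.30, with the share staying that long assumed to be 20 to 30%.

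**The case against.** The strongest reply has four parts.

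*The correlation is chosen where the loss is largest.* This stands. The documents give no value, and the loss shrinks on both sides of 0.20 to 0.30. Any headline number has to carry that condition.

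*The model is idealised.* Only the test within 2 hours is set by protocol. Later testing follows the provider, and low values may be treated, so the nadir is a minimum over an unequal number of readings. This stands as a caution on the size of the gain, and no gain was computed for the 2-hour value. It does not favour the cut: any reading below 40 within 48 hours means that the 48-hour nadir is below 40, so both come from the same readings.

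*The cut has a clinical purpose.* It is the protocol's own definition of hypoglycemia and the event that the study hopes to reduce. That is a good reason to keep it, but not a reason to use it alone.

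*The consequence is small.* The analysis is labelled exploratory, and the plan calls its text a summary of a detailed analysis plan still to be written, so silence on the nadir does not rule it out. A missed association would be called inconclusive, not absent. This stands, and it sets the weight of the point.

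**Conclusion.** The point holds as a modest improvement, not as an error. At a 24% rate and 130 infants, using glucose only as a cut costs roughly 20 to 27 points of power for a true correlation of about 0.20 to 0.30, about 7 to 8 points at 0.10 or 0.40, and about 1 point at 0.50. This rests on bivariate normality, pooled arms, two-sided 0.05 and an assumed correlation.

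A reader might infer more, and the documents do not support it:

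- *That the whole link from cord blood to infant loses this much.* The figure is for glucose only. NICU admission is an event in its own right, and the gain from length of stay is smaller and uncertain. No described form names length of stay, and section 4.4 says that "Neonatal data will be collected through hospital discharge or until 28 days of life".
- *That losses above 30 points follow from a 15% rate.* That is the placebo rate, and every woman randomized here receives betamethasone. Even removing the entire excess in one arm gives 19.5% pooled.
- *That the trial's main result is weakened.* The randomized comparison of C-peptide does not use these outcomes.

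**What to change.** In the Aim 2 text, state that the analytes will be correlated, by ranks or by regression, with two glucose measures: the nadir within 48 hours in mg/dL (item 4 of section 4.6.2 gives no time window, so one should be stated) and the protocol test taken within 2 hours of life. Keep glucose below 40 mg/dL, NICU admission and NICU stay of at least 72 hours as clinical read-outs. Rank-based NICU length of stay, counted as zero for infants not admitted, may be added where the duration is recorded.

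The cost is a sentence or two of wording and slightly more analysis. The glucose measures need no new patients, samples or visits. The downside is that the nadir, like the cut, depends on provider-driven testing and treatment; reporting the 2-hour value beside it shows how far the finding depends on that.

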#### 3.2. Secondary Research Questions

Secondary research questions this study will address are:

- What are other fetal metabolic and hormonal effects of late preterm steroid exposure, compared to no steroid exposure?
- What are other fetal metabolic and hormonal effects of screening for and treatment of BMZ-induced maternal hyperglycemia, compared to usual care (no glycemic control)?
- What is the prevalence of neonatal hypoglycemia in the steroid exposed vs unexposed groups? Does screening for and treatment of steroid-induced maternal hyperglycemia decrease the prevalence of neonatal hypoglycemia?
- What is the degree and duration of neonatal hypoglycemia?
- Does screening for and treatment of steroid-induced maternal hyperglycemia decrease the prevalence of NICU admission?
- What is the effect of timing of delivery on fetal metabolic and hormonal levels?

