### 3.4. Eligibility Criteria

#### 3.4.1. Inclusion Criteria

1. Singleton Pregnancy. A multiple gestation reduced to singleton (either spontaneously or therapeutically) before 14 weeks 0 days by project gestational age (see Section 3.4.2 below) is acceptable.
2. Gestational age at time of 1st dose of betamethasone administration between 34 weeks 0 days and 36 weeks 5 days confirmed by study criteria (see Section 3.4.2 below)
3. Receiving or already received betamethasone for clinical indications within 6 hours of randomization.
4. Likelihood of delivery in the late preterm period (any one of the following):
  - a. Membrane rupture as defined by visible leakage of amniotic fluid from the cervix, Positive AmniSure test, or the presence of any two of the following:
    - i. Pooling of fluid in the vaginal vault
    - ii. Positive nitrazine test
    - iii. Ferning of vaginal fluid
  - b. Preterm labor with intact membranes. Preterm labor is defined as at least 6 regular uterine contractions in 60 minutes and at least one of the following:
    - i. Cervix greater than or equal to 3cm dilated
    - ii. At least 75% effaced
  - c. Maternal or fetal indication for delivery (either by induction of labor or cesarean section) at less than 37 weeks' gestation (e.g. placenta accreta).
  - d. Delivery expected in no less than 12 hours and no more than 7 days, as deemed necessary by the provider. An induction must be scheduled to start by 36 weeks 5 days at the latest, whereas a cesarean delivery must be scheduled by 36 weeks 6 days at the latest.

5. Planned inpatient management until delivery.

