#### **Analysis Plan for Aim 1 (MOTOR subjects not exposed to BMZ vs BMZ-exposed subjects in usual care group):**

Umbilical cord blood C-peptide levels will be compared between controls not exposed to BMZ from the MOTOR study and BMZ-exposed subjects prospectively randomized to usual care, using a linear model. We will estimate

the mean difference between groups along with a 95% confidence interval. For this comparison between controls not exposed to BMZ from the MOTOR study and BMZ-exposed subjects prospectively randomized to usual care, we will adjust for the following potential confounding factors: periodontal treatment in the MOTOR trial, gestational age at delivery, maternal BMI on admission, and fetal gender. Unfortunately we will not be able to accurately ascertain who among the women prospectively enrolled in the randomized trial has periodontal disease, and thus we will not be able to adjust for periodontitis in our analysis. Periodontitis as an unmeasured confounder is unlikely to bias the analysis of our primary outcome, umbilical cord blood C-peptide, but could bias the analysis of other secondary outcomes which are related to inflammation, such as cortisol. We will plan to state this as a limitation of the study in the final manuscript and interpret the results accordingly. A planned subgroup analysis will be performed comparing the BMZ-unexposed controls to women who were randomized to usual care and delivered within 3 days of BMZ exposure. Other 2° outcomes including umbilical cord blood cortisol, insulin-like growth factor, and leptin levels will be tested in similarly. We will not adjust for multiple comparisons, but will present results for all comparisons regardless of “significance.”

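### The delivery-timing model names no baseline covariate, so its arm-specific interval slopes are open to confounding by gestational age at entry and by indication

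*Combined protocol and SAP*

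**What the plan says.** Section 3.2 lists as its last secondary question: "What is the effect of timing of delivery on fetal metabolic and hormonal levels". The Aim 2 analysis plan answers it with "linear regression models to assess the association between randomization arm, time since first dose of BMZ until delivery, doses of BMZ received". The model also lets the interval and dose terms interact with arm. The plan then estimates the associations within each arm and compares them between arms. The outcome is not named in that sentence; I take it to be cord C-peptide and the other cord analytes. No baseline covariate is named.

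Elsewhere the plan does adjust. The Aim 2 primary comparison is made "using a linear model, controlling for gestational age at randomization". Aim 1, which is not randomized, adjusts for "periodontal treatment in the MOTOR trial, gestational age at delivery, maternal BMI on admission, and fetal gender" and calls these potential confounders. The "expected indication for late preterm delivery at trial entry" appears only as a subgroup factor, as does the interval split at three days. Those subgroup analyses are run only if the primary outcome differs between arms.

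Section 3.6 randomizes glucose management only, stratified by site and by two bands of gestational age. Section 3.4.1, under "Likelihood of delivery in the late preterm period (any one of the following", lists membrane rupture, preterm labor, and a maternal or fetal indication. It also lists an expected delivery between 12 hours and 7 days at the provider's judgement, with latest dates of 36w5d for starting an induction and 36w6d for a cesarean.

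**The concern.** The interval from first betamethasone dose to delivery is an observed quantity, and the entry criteria link it to two baseline features. The first is gestational age: a scheduled delivery has a latest date, so a woman who enters late has less time available. The second is the reason for delivery, which governs whether and when delivery is scheduled. If either feature is also related to cord hormones, a slope from the model as written mixes time since betamethasone with differences between the women who deliver early and those who deliver late.

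The time course is central to the protocol's reasoning. Section 2.3 describes a transient maternal hyperglycemia lasting 3 to 4 days. Section 5.1 places the greatest benefit in the first three days, and section 2.4 presents the study as groundwork for a larger trial. A difference between entry groups that is read as a fading response could misplace the window such a trial would target.

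**Working it through.** The documents give no figure for the timing analysis, so there is none to reproduce. The check has four parts.

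**1. Model terms side by side**

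| Analysis | Exposure randomized? | Baseline adjustment named |
|---|---|---|
| Aim 1 | No | Periodontal treatment, gestational age at delivery, BMI, fetal sex |
| Aim 2 primary | Yes | Gestational age at randomization |
| Aim 2 timing | Arm yes; interval and doses no | None |

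The interactions with arm let the slopes differ by arm but do not control for baseline differences. Doses received is settled after entry and may itself depend on the interval, so it does not stand in for a baseline covariate.

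**2. Gestational age**

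Gestational age at delivery = gestational age at first dose (E) + interval (I). Suppose the outcome changes by b per day since betamethasone and by g per day of gestational age at delivery. Then the outcome is bI + g(E + I) = (b + g)I + gE. If E is left out, the slope on I becomes b + g + g × cov(E, I)/var(I). The last term comes only from differences between women in entry age, and it is zero only if E and I are uncorrelated or g is zero.

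The scheduling limits suggest that they are correlated. A cesarean patient entering at 36w3d has at most 3 days to 36w6d, whereas one entering at 34w0d can have the full 7. As an assumption, take entry uniform from 34w0d (day 238) to 36w5d (day 257), and interval uniform from 0.5 days to the smaller of 7 and 258 − E. The correlation of E with I is then about −0.34 for scheduled deliveries. The limit starts to bind at 258 − 7 = day 251 (35w6d), inside the upper randomization stratum, so a two-level stratum term would not capture it.

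**3. Indication, by formula**

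Assume two equal entry groups (p = 0.5), no true time effect, mean intervals differing by *gap*, within-group interval SD *s*, and C-peptide differing by *d* for reasons other than time. None of these values is in the documents.

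Spurious slope = p(1 − p) × gap × d / [p(1 − p) × gap² + s²].

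The standard error of an arm-specific slope is about 1.5 / (√65 × S), with S = √(0.25 gap² + s²). It uses the SD of 1.5 in the bold row of Table 4 and 130/2 = 65 women per arm. Adjusting for the group multiplies that standard error by about S/s.

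| Gap (days) | s (days) | Slope, d = 0.25 | Slope, d = 0.5 | SE of slope | S/s |
|---|---|---|---|---|---|
| 1.5 | 1 | 0.060 | 0.120 | 0.149 | 1.25 |
| 1.5 | 2 | 0.021 | 0.041 | 0.087 | 1.07 |
| 3 | 1 | 0.058 | 0.115 | 0.103 | 1.80 |
| 3 | 2 | 0.030 | 0.060 | 0.074 | 1.25 |

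Slopes and standard errors are in mcg/L per day. The slopes run from 0.021 to 0.120, or 0.06 to 0.36 mcg/L over three days. Relative to the standard error they run from 0.021/0.087 = 0.2 to 0.115/0.103 = 1.1. With the Table 4 SD of 0.75 these ratios double.

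**4. Indication, by simulation**

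A separate simulation used n = 130, SD 1.5, mean 2.85 mcg/L and 2,000 replicates. The true slope was zero, and the model had arm, interval and their interaction but no dose terms. A binary indication with 50% prevalence shifted C-peptide by ±0.5 or ±1.0 mcg/L. The overall share delivering within three days was held at the 70% of section 5.1.

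| P(delivery within 3 days) by indication | Mean usual-care slope without indication | Rejection at 5% |
|---|---|---|
| 0.7 v 0.7 | about 0 | 4.2–6.0% |
| 0.8 v 0.6 | ±0.026 to ±0.057 | 5.6–8.0% |
| 0.9 v 0.5 | ±0.053 to ±0.110 | 6.9–15.6% |

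The simulation error of a 5% rate is √(0.05 × 0.95/2000) = 0.5 percentage points, so the lowest of these rates cannot be told apart from 5%. Adding the indication returned the mean slope to about zero in every case.

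**The case against.** The best defense is that the analysis text calls itself a summary and promises a detailed SAP before first enrolment, where a covariate list for a secondary model would belong. That makes the point easy to settle. However, the summary names covariates for both main comparisons and spells out the timing model's terms without any, so a reader following it would fit an unadjusted model.

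Other objections stand and limit the point:

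- A reader might infer that the fade over time *is* confounded. The documents show only that it can be. They do not say how long each entry group takes to deliver or how cord C-peptide differs between groups. If indication is unrelated to interval, there is no bias from that source.
- A reader might infer that the comparison of slopes between arms is equally exposed. It is not. Arms are randomized, so confounding common to both largely cancels when the slopes are subtracted, provided that arm does not change the interval and the indication effect is similar in both arms. Nothing in the documents suggests otherwise.
- A reader might infer that the analysis plan makes a causal claim. Its timing paragraph speaks of associations throughout; the word *effect* is in the research question. The gap lies between that question and an unadjusted model.
- Aim 1 is an imperfect parallel. It compares trial women with stored samples from another study and does not adjust for indication. BMI and fetal sex have no evident link to the interval, so the case for them rests on precision and consistency.

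**Conclusion.** The point holds for the arm-specific interval slopes. As written, they mix time since betamethasone with gestational age at entry and with indication, and the plan's own entry criteria supply the link. Size and direction are unknown. The range of 0.02 to 0.12 mcg/L per day rests entirely on assumed group differences of 0.25 to 0.5 mcg/L in C-peptide and 1.5 to 3 days in mean interval. The Table 4 design differences of 0.5 to 1.5 mcg/L give a sense of scale only, because they are differences between arms. Set against the slope's own standard error, the bias could be negligible or could exceed one standard error.

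This is a secondary question. The primary Aim 2 contrast is randomized and does not depend on this model, and no stopping rule uses it. The change is still worth making, because it improves the answer to a stated question using baseline variables the trial already records.

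**What to change.** In the detailed SAP, name the timing outcome and add these to the timing model:

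- gestational age at randomization, in days;
- expected indication at trial entry (membrane rupture, preterm labor, obstetric or medical);
- optionally, maternal BMI and fetal sex, for precision and consistency with Aim 1.

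Do not also enter gestational age at delivery. It equals gestational age at first dose plus interval, and randomization falls close to first dose, so the three terms are nearly collinear. State that the slope at a given entry age still includes the maturation that comes with waiting (b + g in the working).

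Fit one joint model with arm interactions rather than two separate models. The covariate coefficients then draw on about 130 women, although each arm's slope still rests on about 65. Tabulate interval by arm and by indication so that overlap can be seen, and report the slopes as adjusted associations.

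The required terms cost 1 + 2 = 3 degrees of freedom, or 5 with the optional ones. A common covariate effect in both arms is assumed. The main cost is precision: in the illustration above, the standard error of the slope rises by a factor of 1.07 to 1.80, most when indication largely determines the interval. No new data collection and no change to care are needed.
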